Patients who drink large amounts of water during regular dialysis (> 2 glasses, approximately 0.4 L).

The study is discontinued in case of a severe reaction (even if not related to the study), such as the need to interrupt dialysis. The patient or participant may also choose to discontinue participation in the study at any time.

Intervention and Procedures

Patients in need of dialysis and who regularly undergo dialysis at the dialysis unit at Vrinnevi Hospital in Norrköping are asked to participate in the study. Patients who are eligible are those who have fluid removal of either <500 ml or >2000 ml. These patients are approached during a routine dialysis visit to the dialysis unit. If the response is positive, a trial session is planned for a later date.

Before dialysis begins, the patient is weighed. Then, the regular dialysis procedure starts, with the dialysis machine being connected. At the same time, Bioimpedance is also connected to the patient, and values for lean body mass (LBM), fat mass (FM), ECV, and ICV are recorded. Pulse and blood pressure are also recorded. Once the dialysis machine is connected with an intravenous access, the first blood samples, i.e., "zero samples," are taken. Dialysis then commences.

The selected dialysate is recorded, as well as the continuous fluid removal and blood pressure. Blood samples are taken every 30 minutes for 150 minutes (Hb, hematocrit, albumin, Immunoglobulins G and M, and colloid osmotic pressure (COP)), bioimpedance values are recorded, and pulse and blood pressure are registered. This continues until the end of dialysis. At the end of dialysis, the final samples and measurements are taken. The patient is weighed once again.

Fluid intake if it occurs is also recorded. When the patient leaves the dialysis unit, the study concludes.

In case of pressure drops, these are treated in the usual manner, i.e., the patient is placed in the Trendelenburg position or supplemented with Albumin 20%. Measures are recorded.

In total, blood sampling amounts to approximately 50 ml, at most 75 ml, equivalent to 3 to 5 tablespoons.

Measurements

Weight is taken before and after dialysis.

Bioimpedance is connected and values for body composition, i.e., lean body mass (LBM), fat mass (FM), ECV, and ICV are recorded before and after dialysis, as well as during blood sampling.

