Hb, albumin, Ig G + M, and COP are measured and analysed before, at 1, 30, 60, 90, 120, and possibly at 150 minutes after the initiation of hemodialysis, as well as at the end of dialysis. These samples are taken from the access (cannula) used during dialysis. Therefore, no additional punctures are needed.

Fluid removal and any spontaneous diuresis are recorded. Patients with spontaneous diuresis are asked to urinate before and after dialysis.

Oral fluids consumed during dialysis are recorded.

Risk- Benefit assessment

Disadvantage for patients is a loss of approximately 50 to 75 ml of blood, which corresponds to half a decilitre of blood (3 to 5 tablespoons) (about 1% of the total blood volume). In connection with the study, there is enhanced monitoring, and the closer pressure and pulse controls can detect an impending drop in blood pressure slightly earlier.

The advantage of the study is more long-term. The study contributes to mapping how the recruitment of fluid/oedema from the interstitium occurs. Consequently, one should be able to more easily predict potential drops in blood pressure by taking preventive measures such as adjusting composition of dialysate and rate at which the hemodialysis is performed.

Treatment and administration of other medications

Hemodialysis is performed according to standard procedures. No restrictions on the administration of medications or treatments will be made, except for a selection of patients who do not drink more than 2 glasses, approximately 0.4 litres of water, during regular dialysis sessions.

The study does not affect the patient's ongoing care or management.

Studied data/Registration of effects

Changes in Hemoglobin, albumin, and COP during hemodialysis

Changes in plasma volume are calculated partly using changes in Hemoglobin and partly using Mass Balance calculations.

Once all samples are analyzed, any remaining blood/plasma is destroyed.

Mass balance

Plasma volume. Initial blood volume calculated with the Nadler formula ⁷.

BV_0 , based on height h , (meters), weight w (kg) and gender.

Men: $BV_0 = 0.3669 h^3 + 0.03219 w + 0.6041$

Female: $BV_0 = 0.3561 h^3 + 0.03308 w + 0.1833$

How mass balance calculations will be performed is described in a work on 5% albumin solution. ^{5,6}. Total mass hemoglobin at study start is calculated from BV_0 and hemoglobin at start of hemodialysis, Hb_0 ; ⁷

$$MHb_0 = BV_0 \times Hb_0$$

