Blood volume (BV) at a later occasion, t , is calculated in a similar manor;

$$BV_t = \frac{MHb_t}{Hb_t}$$

Plasma volume (PV) is calculated;

$$BV_t (1 - Hct_t) = PV_t$$

The percentage increase/decrease in plasma volume will then be ($\Delta PV\%$);

$$\frac{PV_t - PV_0}{PV_0} \times 100 = \Delta PV\%$$

Recruited fluid (RE) from the tissue is based on the change in plasma volume and total diuresis/fluid removal. However, this volume must be corrected for diuresis and ingested fluid.

$$RE_{extravascular} = Ultrafiltrate + Diuresis - Ingested + (PV_t - PV_0)$$

Statistics and Data Processing

The study aims to follow a fluid kinetic process. In previous studies, we routinely used 10 healthy subjects to study similar processes. This has been sufficient to describe clear trends and differences in how the body responds to fluid infusions. However, in this study, we increase the number of participants to fifteen in each group to even more clearly establish the processes.

As there are only two groups to be compared, a t-test will primarily be used for the primary variable, i.e., the effect on plasma volume. For secondary variables, chi-square tests will be used. In the case of non-normally distributed data, Wilcoxon's test will be used instead.

Safety Regulation

The study will be conducted according to the protocol and applicable regulations, LVFS 2011:19, ICH GCP, and the latest version of the Helsinki Declaration. Patients will be monitored in the usual manner in the dialysis department.

Quality Assurance

- relevant health status data from medical records or health declaration
- signed consent
- The study is conducted in accordance with the protocol

Study Director [name] participated in a GCP course at Linköping University Hospital on April 25 - 26, 2007, and subsequently conducted several studies approved by the Medical Products Agency.

Ethics

Patients are approached for participation in a calm stage when they are receptive to information. If there is potential interest from the patient to participate, the study investigator informs the patient about the study. The responsible physician obtains the patient's written consent, and a copy of the signed consent form is provided to the patient.

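### The recruitment formula has no term for circuit fluid, so any priming fluid returned after the zero sample is counted as tissue recruitment; this matters most for the level in the <500 ml group

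*Protocol*

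**What the plan says.** Protocol, Intervention and Procedures, gives the order at the start: "Once the dialysis machine is connected with an intravenous access, the first blood samples, i.e., 'zero samples,' are taken. Dialysis then commences". For the end of the session it says: "At the end of dialysis, the final samples and measurements are taken. The patient is weighed once again". It does not place either step relative to rinse-back of the circuit.

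Protocol, Measurements, lists the blood samples as "measured and analysed before, at 1, 30, 60, 90, 120, and possibly at 150 minutes after the initiation of hemodialysis", plus one at the end of dialysis. The 1-minute sample is given no stated purpose.

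Protocol, Mass balance, sets the baseline: "Initial blood volume calculated with the Nadler formula", a patient volume with no circuit component, and "Total mass hemoglobin at study start is calculated from BV_0 and hemoglobin at start of hemodialysis, Hb_0". It does not say whether Hb_0 is the pre-dialysis or the 1-minute sample. Recruitment is "RE_{extravascular} = Ultrafiltrate + Diuresis - Ingested + (PV_t - PV_0" (closing bracket not included in the quote). The only correction described is: "However, this volume must be corrected for diuresis and ingested fluid".

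Neither document mentions priming fluid, its volume, whether it is returned or discarded, or rinse-back. The recorded fluid items are machine removal, urine and drinks.

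**The concern.** The mass balance reads every fall in hemoglobin relative to baseline as fluid entering plasma, and assigns to the tissues whatever recorded intake and output do not explain. Priming fluid that reaches the patient after the zero sample dilutes hemoglobin in the same way. The formula has nowhere else to put it, so it is booked as tissue recruitment.

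The first aim in Purpose and Objectives is how much fluid leaves the interstitium depending on whether removal is needed. In the <500 ml group the true volume may be only a few hundred ml, so a fixed offset can be a substantial part of the reported figure. The study could then describe recruitment in patients with little fluid removal when part of the dilution came from the machine. The proportion by route, listed as primary in the protocol's Outcome Measures, is also exposed: fluid without protein would look like fluid crossing the capillary wall.

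**Working it through.** **The plan's own figure.** The only calculated figure is the sample size in SAP 1.4: difference 25%, SD 20%, two-sided 0.05, power 80%. The normal approximation gives 2 × (1.960 + 0.842)² × (20/25)² = 10.05, rounded up to 11 per group, as stated. This point does not alter it.

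**Inputs from the documents.** BV_t = MHb_t/Hb_t; PV_t = BV_t(1 − Hct_t); the RE formula; the Nadler equations; group limits of <500 ml and >2000 ml.

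**Assumed inputs.** Returned prime V = 150-250 ml, or 0 if discarded; hemoglobin mass unchanged by the prime; prime free of protein and red cells; the zero sample used as Hb_0.

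**Step 1, the identity.** With V returned after the zero sample, the plasma balance is

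PV_t − PV_0 = RE_true + Ingested + V − UF − Diuresis,

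so RE_true = UF + Diuresis − Ingested − V + (PV_t − PV_0). The written formula omits −V, so RE_written = RE_true + V once the prime has mixed. This also holds if some prime later leaves the plasma, because that loss then appears as lower net recruitment.

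**Step 2, a numerical check.** Take an assumed man of 1.75 m and 80 kg with Hb 110 g/L and Hct 0.33.
- BV_0 = 0.3669 × 1.75³ + 0.03219 × 80 + 0.6041 = 5.15 L
- PV_0 = 5.15 × 0.67 = 3.45 L
- With V = 200 ml and no tissue recruitment, Hb becomes 110 × 5.15/5.35 = 105.9 g/L, and PV rises by 200 ml (+5.8%). The formula returns RE = 200 ml; the true value is 0.

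**Step 3, share of apparent RE.** The share is V/(RE_true + V), taking RE_true = UF for illustration.

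| RE_true (ml) | V = 0 | V = 150 ml | V = 250 ml |
|---|---|---|---|
| 300 | 0% | 150/450 = 33% | 250/550 = 45% |
| 500 | 0% | 150/650 = 23% | 250/750 = 33% |
| 2500 | 0% | 150/2650 = 6% | 250/2750 = 9% |

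**Step 4, between-group difference in ml.** (RE_B + V) − (RE_A + V) = RE_B − RE_A. Adding one constant to every patient changes neither the t-test nor the Wilcoxon test. If mean V differed between groups, the difference in ml would be biased by that difference.

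**Step 5, lymph/capillary proportion.** The documents give no formula for the split. If prime is read as capillary fluid, the apparent lymph share is L × RE_true/(RE_true + V). With an assumed true L = 50% in both groups and RE_true = 2000 ml in the high-removal group:

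| V (ml) | Low group, RE 300 ml | Low group, RE 500 ml | High group, RE 2000 ml | False gap (points) |
|---|---|---|---|---|
| 0 | 50.0% | 50.0% | 50.0% | 0 |
| 150 | 33.3% | 38.5% | 46.5% | 13.2 or 8.1 |
| 200 | 30.0% | 35.7% | 45.5% | 15.5 or 9.7 |
| 250 | 27.3% | 33.3% | 44.4% | 17.2 or 11.1 |

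The first gap in each row is for 300 ml in the low group, the second for 500 ml. The gaps scale with L, so a true share of 25% would halve them.

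**The case against.** The strongest reply is that the deciding fact is absent. The documents do not say that prime is returned, and if it is discarded nothing is wrong. That stands: every size above is conditional and the range starts at 0. The plan also does not record the fact, so readers could neither rule the error out nor correct it.

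Second, Hb_0 is defined only as hemoglobin at the start of hemodialysis, and a 1-minute sample is planned. If that sample were the baseline, much of the dilution would already lie in it, provided mixing were complete. This also stands. But the pre-dialysis draw is the one the protocol labels as zero, so it is the natural reading, and the ambiguity itself needs settling.

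Third, SAP 1.2.1 and 1.3 make fluid recruitment the primary variable, and an equal offset drops out of that comparison in ml. A reader might infer that the primary group comparison is invalid; the documents do not support that. Hemodialysis follows standard procedures at one unit, and nothing suggests that prime is handled differently by group.

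Fourth, the route proportion is primary in the protocol but falls in the secondary analysis of the SAP, and its method is not given. The size in Step 5 is therefore an illustration.

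Three further inferences also fail:
- **Share of ultrafiltration.** Dividing prime by ultrafiltration gives larger percentages, but the outcome is RE.
- **Comparison with the 25% in the sample size.** The plan gives that 25% no denominator, and recruited over removed is not a defined outcome.
- **Recruitment rate from 1 to 30 minutes.** A constant offset cancels from RE(30) − RE(1) unless mixing is incomplete at 1 minute.

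**Conclusion.** The point holds conditionally. If prime is returned and the zero sample is Hb_0, RE is overstated ml for ml by the returned volume at every mixed time point. That follows from the protocol's own formula. Its relative size rests on two assumptions that the documents do not settle, namely the volume returned and true RE close to ultrafiltration. Other true volumes would change the percentages, and diuresis also enters RE.

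Two results remain exposed: the absolute recruitment level in the <500 ml group, and the lymph/capillary proportion if protein-free prime is attributed to the capillary route. It would be wrong to conclude that prime is a large share of the signal in every case. The end of the session is a smaller matter: the order of the final sample and rinse-back is simply unstated, and nothing says that sampling follows rinse-back.

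**What to change.** - In Mass balance, state which sample is Hb_0.
- In Intervention and Procedures, record for each session whether prime is returned or discarded, and its volume. This asks for recording only, not for a change in how the circuit is handled.
- When the pre-dialysis sample is the baseline, subtract returned prime from RE at all t > 0.
- State that the final blood sample is drawn before rinse-back.
- As a sensitivity analysis, repeat the calculation with the first post-mixing sample as baseline (1 minute, or 30 minutes if mixing is incomplete). Do not also subtract prime in that run, or it would be removed twice.

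The cost is one or two CRF fields, one term in the formula, a sentence on the order of the last sample, and one extra analysis run on samples already planned. The drawback is that prime volume comes from the circuit specification and is known only approximately.

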The alternative hypothesis is that we find a clinically relevant difference in fluid flows from the tissues and the pathway of fluid recruitment to the bloodstream.

Outcome Measures

Primary outcome variables are:

Recruitment of fluid from the interstitium calculated from fluid removal and hemoglobin changes.^{5,6}

Proportion of recruited fluid via lymph or via capillary/venular walls based on fluid recruitment and changes in plasma albumin and immunoglobulins G and M.

Secondary outcome variables are:

Weight, blood pressure and changes in bioimpedance variables.

Study Design

Open-label, prospective clinical observational study, where patients are divided into two groups. One group patients with sufficient urine production and dialysis performed solely to "purify" the blood, and another group without or with minimal urine production, who, in addition to blood purification, are in need of a significant fluid removal.

Number of Patients

The study population consists of 15 patients with minimal fluid removal during dialysis and 15 patients in need of fluid removal exceeding 2000 ml.

According to earlier experience, 15 patients in each group should be sufficient to clearly observe a pattern in fluid recruitment from the tissues (lymph or pericapillary fluid). For 80% power at 25% difference in fluid recruitment balance between the groups and a standard deviation of 20%, at least 11 patients should be recruited to each group to achieve a significance level below 0.05 with a T-test or Wilcoxon (if the material is not normally distributed).

Recruitment and Consent

Patients receiving hemodialysis regularly at the dialysis department at Vrinnevi Hospital in Norrköping are screened if they are expected to meet the inclusion criteria for the study.

Those who meet the inclusion criteria and have no exclusion criteria to participate are asked for participation and consent. Consent is obtained by one of the investigators verbally and in writing, during a hemodialysis session prior to the actual study procedure.

Inclusion Criteria:

Patients receiving hemodialysis (<500 ml or >2000 ml ultrafiltration):

Signed informed consent that the patient accepts participation in the study after oral and written information.

Exclusion Criteria:

Patients who may be affected by blood sampling, i.e., have low hemoglobin concentration, independent of dilution before dialysis (Hemoglobin 85 g/L).

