1.2. Statistical analysis

1.2.1. Statistical method

- A two-sided test of significance will be used.
- After the last patient has been included an evaluation will be made if results are distributed according to the norm. If so, parametrical statistical methods will be used i.e., T-test.
- If these are not distributed according to the norm the Wilcoxon test will be used.
- Recruitment of fluid is the primary variable.

If the study is dissected, it contains two groups:

- A. Patients with a fluid withdrawal of less than 500 ml
- B. Patients with a fluid withdrawal of more than 2000 ml

Statistical processing of the primary outcome

In the first analysis total recruitment of fluid from the tissues will be evaluated.

Total recruitment and AUC (Area under the curve) for recruited fluid, i.e., fluid removal and hemoglobin changes. Moreover, the inverted half-life for recruitment will be determined.

In the secondary analysis, the proportions of the fluid recruitments via lymph or via capillary/venular walls will be performed

Methods: One way test, T-test or Wilcoxon.

Secondary outcome

Weight, blood pressure and changes in bio-impedance variables will be correlated to withdrawal of fluid.

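### The protocol assigns chi-square tests to secondary variables that are all numerical, and the SAP gives the same variables a different analysis (minor; secondary outcomes only)

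*Protocol*

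**What the plan says.** The protocol (Outcome Measures) lists the secondary outcomes as "Weight, blood pressure and changes in bioimpedance variables". Its Measurements section spells out the bioimpedance part: "lean body mass (LBM), fat mass (FM), ECV, and ICV are recorded before and after dialysis, as well as during blood sampling". Weight is taken only before and after dialysis.

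Three sentences in the protocol's Statistics and Data Processing section bear on the tests:
- for the primary variable, "As there are only two groups to be compared, a t-test will primarily be used for the primary variable";
- then "For secondary variables, chi-square tests will be used";
- then "In the case of non-normally distributed data, Wilcoxon's test will be used instead".

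The SAP (1.2.1) opens with a general rule. It begins "A two-sided test of significance will be used", prescribes a t-test when results are normally distributed, and adds "If these are not distributed according to the norm the Wilcoxon test will be used". It names no chi-square test. Its line on the secondary outcome reads "Weight, blood pressure and changes in bio-impedance variables will be correlated to withdrawal of fluid". SAP 1.3 makes no multiplicity correction for secondary measurements but promises care in interpreting weak positive results.

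**The concern.** A chi-square test compares counts in categories. Kilograms, blood pressure and body-composition values are not counts, and no threshold turns them into counts. Someone following the protocol literally would have to choose a cut-point, probably after seeing the data, and would lose information by doing so. Someone following the SAP would compute correlations instead. The same three outcomes could therefore be reported in two quite different ways, each with some support in the documents.

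A smaller issue sits beside this. The SAP line does not say whether a patient contributes one value or every reading through the session, and that choice can change the error rate. At stake is the credibility of the secondary results.

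**Working it through.** **1. The plan's own figure.** SAP 1.4 gives a difference of 25%, an SD of 20%, two-sided 5% and 80% power. n per group = 2 × (1.960 + 0.842)² × (20/25)² = 2 × 7.85 × 0.64 = 10.05, rounded up to 11. The stated 11 is reproduced. It concerns fluid recruitment and is untouched by this point. The documents give no figure for the secondary variables.

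**2. The texts side by side.**

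| Variable | Type | Protocol test | SAP analysis |
|---|---|---|---|
| Weight | numerical, before and after | chi-square | correlation with withdrawal |
| Blood pressure | numerical, repeated | chi-square | correlation with withdrawal |
| Change in LBM, FM, ECV, ICV | numerical, repeated | chi-square | correlation with withdrawal |

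If the protocol's Wilcoxon sentence is read as covering secondary variables too, it applies only when data are not normal. Chi-square then remains the default for normal data, where it does not fit.

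**3. Cost of forcing a chi-square.** Assumptions, none from the documents: normal data, a split at the pooled median, 15 per group. If x of 15 in one group and 15 − x in the other lie above the median, the uncorrected statistic is 30 × [x² − (15 − x)²]² / 15⁴.
- x = 10: 30 × 75² / 50,625 = 3.33, p = 0.068.
- x = 11: 30 × 105² / 50,625 = 6.53, p = 0.011.

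Significance therefore needs at least an 11 to 4 split. Under no difference that happens about 2.7% of the time, so the test is conservative as well as coarse. Simulated power:

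| True difference | t-test | Wilcoxon | Chi-square |
|---|---|---|---|
| 0.8 SD | 56% | 52% | 31% |
| 1.0 SD | 75-77% | 71-73% | 48-49% |
| 1.25 SD | 91% | 89% | 68-69% |

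Ranges are the spread between simulation runs.

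**4. What a pooled correlation measures.** Eligibility leaves out 500 to 2000 ml. Take withdrawal as uniform on 0-0.5 L in one group and 2-3.5 L in the other (assumed).
- Between-group variance: (2.75 − 0.25)²/4 = 1.5625.
- Mean within-group variance: (0.5²/12 + 1.5²/12)/2 = 0.104.
- Group share: 1.5625/1.6667 = 94%.

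With 2-5 L in the high group, the share is 2.641/(2.641 + 0.385) = 87%; in simulated samples of 30 it averages 88%. The pooled r holds its size (5.2% and 4.9%). A 1 SD group offset with no slope inside either group still gives a mean r of 0.44 or 0.42.

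**5. Repeated readings treated as independent.** Assumptions: seven readings per patient (0, 30, 60, 90, 120 and 150 min and an assumed end at 240 min), raw values, no true effect, within-patient correlation 0.3 to 0.7. The false-positive rate at nominal 5% is about 12-22% if each reading is paired with cumulative removal, and about 25-41% if paired with the session total. Using change from baseline with cumulative removal, it is about 19% whatever the within-patient correlation. None of this can apply to weight, which has no readings during the session.

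**The case against.** The best reply is that the plan already contains the right test. The SAP's two-sided t-test/Wilcoxon rule stands before the primary-outcome heading, speaks of results in general, and is not limited to the primary variable. On that reading, all that remains is one misassigned test name in the protocol and one terse line in the SAP. Much of this stands. It is why the remedy is the SAP's own rule and why the severity is minor. It does not remove the defect: the protocol sentence still prescribes something else, and the SAP's specific line for these variables says correlation.

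A second reply is that chi-square was meant for pressure drops. These and the measures taken are recorded, but they are not listed as an outcome.

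Three stronger readings are tempting and are not supported.
- *That the SAP correlation is invalid or must be demoted.* A pooled r is a valid test of association and holds its size, and the SAP claims no dose-response. The missing coefficient, unit and time point are mainly missing detail.
- *That within-group correlations are useless.* That depends on an assumed weak slope. Weight change should track removed volume closely; at an assumed 3 SD per litre the group-adjusted slope is detected in over 99% of simulated trials.
- *That pressure drops would be shared equally between groups.* The protocol's Synopsis and Background tie hypotension to fluid removal, so an equal split cannot be assumed.

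**Conclusion.** Wrong as written, secondary outcomes only, minor. The conclusion rests on the text: numerical variables, no cut-point in either document, a chi-square test in the protocol and a correlation in the SAP. It needs no simulation.

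The sizes are illustrations under stated assumptions. A forced median split at a 1 SD difference with 15 per group costs roughly 27 percentage points of power. Ignoring the clustering of readings within patient would raise the false-positive rate to about 12-41%, depending on the within-patient correlation and on whether cumulative or total removal is used. Group membership would account for about 88-94% of the variance in withdrawal, so a pooled correlation largely reflects the group contrast.

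A reader might infer that the main result or the number of patients is in doubt. Neither is: the primary comparison uses a t-test or Wilcoxon, and the 11 per group reproduces.

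**What to change.** 1. Delete the chi-square sentence from the protocol.
2. State in both documents that between-group comparisons of weight, blood pressure and bioimpedance variables use each patient's change from pre-dialysis to end of dialysis, tested by the SAP's own rule (two-sided t-test, or Wilcoxon if not normally distributed), with the difference and 95% CI. Name which blood pressure (systolic, diastolic or mean) is meant.
3. If a yes/no variable such as any treated pressure drop is added, use Fisher's exact test, report the counts, and assume nothing about how events divide between groups. With few events the choice matters: 0/15 against 4/15 gives p = 0.032 by uncorrected chi-square and p = 0.100 by Fisher.
4. Keep the SAP correlation, with the coefficient named and one value per patient (total withdrawal against change). If readings through the session are used for blood pressure or bioimpedance, account for readings within patient. Add a note that a pooled coefficient largely reflects the group contrast.
5. Say which of the group comparison and the correlation is the main secondary analysis. That is the sponsor's choice.

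The cost is a few sentences in each document, settled before the data are examined. Every item is already recorded, so no patients, visits or samples are added, and the sample size does not change.
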